15 DATA SAFETY AND MONITORING BOARDS

All trials initiated by the Brown University Oncology Research Group (BrUOG) are subject to oversight by the Data Safety Monitoring Board (DSMB). This board meets two times per year with any additional meetings scheduled when needed. The responsibilities are as follows:

- Familiarize themselves with the research protocol (s)
- The DSMB reviews trial performance information such as accrual information.
- Review interim analyses of outcome data and cumulative toxicity data summaries to determine whether the trial should continue as originally designed, should be changed, or should be terminated based on these data.
- The DSMB also determines whether and to whom outcome results should be released prior to the reporting of study results.
- All adverse events are reviewed by the committee, with assurances that these have been in fact sent for review to all pertinent IRBs.
- Review of reports of related studies to determine whether the monitored study needs to be changed or terminated.
- Review major proposed modifications to the study prior to their implementation (e.g., termination, dropping an arm based on toxicity results or other reported trial outcomes, increasing target sample size).
- Following each DSMB meeting, provide the study leadership with written information concerning findings for the trial as a whole related to cumulative toxicities observed and any relevant recommendations related to continuing, changing, or terminating the trial.

The study leadership will provide information on cumulative toxicities and relevant recommendations to the local principal investigators to be shared with their IRB's.

16 STATISTICAL CONSIDERATIONS

16.1 Study Design/Endpoints

The primary endpoint of this pilot study is to assess the acute toxicity of combining nivolumab with definitive chemoradiation. For the purposes of the study, acute toxicities will be those having onset during or within 30 days of completing treatment. For those receiving nivolumab as maintenance treatment, it will also include those events occurring during or within 30 days of

BrUOG 355: 7/8/17, 7/11/17, 7/20/17, 8/7/17, 8/8/17, 8/14/17, 8/16/17, 8/21/17, 8/22/17, 8/24/17, 8/28/17, 9/5/17, 9/6/17, 9/8/17, 9/11/17, 11/7/17, 11/8/17, 11/19/17 approved DD, 11/20/17, 12/12/17, 12/14/17, 1/29/18, 2/1/18, 2/6/18, 2/7/18, 2/8/18, 2/9/18, 2/12/18, 2/13/18, 3/8/18 all reviews, 3/9/18, 3/13/18, 3/14/18, 3/15/18, 4/19/18, 4/23/18, 5/29/18, 6/5/18, Amendment # 1 7/9/18, Amendment # 2 12/12/18, Amendment #3, 4/6/2020, Amendment #4 5/11/2020

treatment completion.

16.1.1. Safety review

A safety review for each cohort will be conducted. For cohort 1, safety analysis will occur at the end of chemoradiation. For patients in cohort 2 (who receive nivolumab following chemoradiation), evaluation for safety will occur 4 weeks following initiation of maintenance nivolumab. For patients in cohort 3, safety analyses will occur at the end of chemoradiation and after maintenance therapy has completed.

Criteria that will determine safety will include:

- Grade 3 or higher adverse events that persists for 14 days or longer despite dose-holds and/or maximal medical support. This excludes uncomplicated neutropenia and any laboratory abnormalities deemed by the treating clinician as having no clinical significance
- Inability to complete chemoradiation within 8 weeks

The BrUOG overall PI, the Women & Infants' Hospital site PI (once study is activated), and the Medical Director of BrUOG will review safety data as described to make determinations of feasibility. Enrollment to cohort 2 will not be dependent on the safety review for cohort 1. However, the safety review will be completed for cohort 2, before enrollment begins in cohort 3.

If more than 25% of patients (more than 2 patients in cohort 1 or more than 1 patient in cohort 2) experience a grade 3 or higher adverse event that persists for 14 days or longer, despite dose-holds and/or maximal support, the treatment will be considered not feasible and the next cohort will not be opened.

If more than 25% of patients (more than 2 patients in cohort 1 or more than 1 patient in cohort 2) are unable to complete chemoradiation within 8 weeks, the treatment will be considered not feasible and the next cohort will not be opened.

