16.2 Sample Size, Accrual Rate and Study Duration

For this feasibility study, the planned sample size is 24 patients (8 in cohorts 1 (1A and 1B)), 4 in cohort 2, and up to 12 in cohort 3 to enroll a maximum of 24 evaluable patients in the trial). The total sample size may need to be adjusted to allow for replacement of participants who withdraw prior to completion of the third week of chemoradiation, as these are the only reasons for replacement. It is anticipated that 4 patients will be enrolled per month for an approximate accrual period of 9 months. All patients who begin protocol therapy will be included in the evaluation of toxicity for 30 days post last treatment, unless patient withdraws from study.

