16.4 Analysis of Primary Endpoints

Time-to-event endpoint of progression free survival at 3 years will be described using the method of Kaplan-Meier, and presented with 90% confidence intervals. Patients that are alive without disease progression at time of analysis are censored at the date of last disease evaluation. Acute Treatment-related toxicities that occur during and within six months of study treatment will be summarized by maximum grade and by term using CTCAE v4.0 and reported with 90% binomial exact confidence intervals. Acute toxicities will be used to determine the feasibility within each cohort.

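### The cohort 1 safety analysis is set before its own 14-day and 30-day windows can close, and nothing requires the matured cohort 1 data to be used before cohort 3 opens

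*Combined protocol and SAP*

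**What the plan says.** **Timing and criterion (16.1.1).** The plan states: "For cohort 1, safety analysis will occur at the end of chemoradiation". One of its two safety criteria is: "Grade 3 or higher adverse events that persists for 14 days or longer despite dose-holds and/or maximal medical support", with exclusions for uncomplicated neutropenia and laboratory findings of no clinical significance. More than 2 of 8 such patients in cohort 1 makes the treatment not feasible. No data cut is given, and no rule for events still open at the review.

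**Acute window.** Section 16.1 says that "acute toxicities will be those having onset during or within 30 days of completing treatment". Section 16.2 adds: "All patients who begin protocol therapy will be included in the evaluation of toxicity for 30 days post last treatment". Section 16.4 says: "Acute toxicities will be used to determine the feasibility within each cohort", but describes acute toxicity as running to six months after treatment.

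**What opens each cohort.** Section 16.1.1 says: "Enrollment to cohort 2 will not be dependent on the safety review for cohort 1". It continues: "However, the safety review will be completed for cohort 2, before enrollment begins in cohort 3". Section 5.4 opens cohort 3 once safety is confirmed in cohorts 1 and 2, without saying on what follow-up. Sections 5.4 and 16.3 let cohort 1 results alter cohort 3, and Section 15 gives the DSMB a general power to change or stop the trial. None of these sets a maturity condition.

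**The concern.** At a patient's own end of chemoradiation, none of her 30 post-treatment days has been seen. A grade 3 event that began in the last 14 days of treatment cannot yet have met the persistence criterion. An early count can therefore equal the full count or fall below it, never exceed it, so any error favours passing.

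The decision matters because cohort 2 receives chemoradiation without concurrent nivolumab. Cohort 1 is thus the only evidence on the concurrent combination before up to 12 more patients receive it in cohort 3, followed by maintenance. The 8-week completion criterion is not affected by this point.

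**Working it through.** **1. The plan's own threshold.** More than 25% of 8 means at least 3 (2/8 = 25%, 3/8 = 37.5%). More than 25% of 4 means at least 2 (1/4 = 25%, 2/4 = 50%). Both match the counts in 16.1.1.

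**2. Follow-up needed.** An onset on day 30 after treatment (16.1) needs 14 more days to be classified (16.1.1): 30 + 14 = 44 days after chemoradiation.

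**3. Follow-up available at one review, held when patient 8 finishes.** Even accrual and equal treatment lengths are assumed. Section 16.2 says: "It is anticipated that 4 patients will be enrolled per month for an approximate accrual period of 9 months". That product is 36 patients against a planned 24, so two rates are used, plus a slower one. Spacing s is 30.4/4 = 7.6 days, 9 × 30.4/24 = 11.4 days, or 30.4/2 = 15.2 days. Patient i has (8 − i) × s days since her own end of chemoradiation.

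| Accrual | Under 44 days | Under 30 days | Under 14 days |
|---|---|---|---|
| 4 per month | 6 of 8 | 4 of 8 | 2 of 8 |
| 24 in 9 months | 4 of 8 | 3 of 8 | 2 of 8 |
| 2 per month | 3 of 8 | 2 of 8 | 1 of 8 |

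**4. Effect on the chance of passing.** This is illustrative, because the documents give no toxicity rate or onset pattern. Assume a constant hazard over 28 days of induction + 42 of chemoradiation + 30 after = 100 days. With one review and open events followed to outcome, the onset days counted for patient i are d_i = 70 + min(30, (8 − i) × s). Her captured probability is 1 − (1 − p)^(d_i/100). The chance of passing is the probability that 2 or fewer of 8 qualify.

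Example at p = 0.40 and s = 7.6: patients 1 to 4 have 0.400. Patients 5 to 8 have d = 92.8, 85.2, 77.6 and 70, giving 0.378, 0.353, 0.327 and 0.301. The chance of passing is 0.381. With full data it is 0.0168 + 0.0896 + 0.2090 = 0.315.

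| True rate | Full data | One review, s = 11.4 | One review, s = 7.6 |
|---|---|---|---|
| 20% | 0.797 | 0.825 | 0.833 |
| 30% | 0.552 | 0.598 | 0.613 |
| 40% | 0.315 | 0.364 | 0.381 |
| 50% | 0.145 | 0.181 | 0.194 |

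Less favourable readings at 40%:
- One review, open events left out: 0.415 to 0.457.
- Each patient cut at her own end, open events followed (70 of 100 days counted): 0.550.
- Each patient cut at her own end, open events left out (56 of 100 days counted): 0.682.

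**5. Calendar.** Day 0 is the last cohort 1 patient's first dose. Inputs are the second induction dose on day 14, then 7 to 21 days to chemoradiation (5.4), 42 to 60 days of radiation (5.6, 5.7), and for cohort 2 a 14 to 21 day gap (5.4) plus 28 days (16.1.1).
- Cohort 1 data complete: 14 + (7 to 21) + (42 to 60) + 44 = day 107 to 139.
- Cohort 2 review: 14 + (7 to 21) + (42 to 60) + (14 to 21) + 28 = 105 to 144, plus a lag for enrolling 4 patients of 4 × 7.6 = 30.4 or 4 × 11.4 = 45.6 days. That is about day 135 to 174, or 151 to 190.
- At equal treatment lengths, the cohort 2 review falls lag + (14 to 21) + 28 = 72 to 79 or 88 to 95 days after the last cohort 1 patient ends chemoradiation. Subtracting 44 leaves 28 to 35 or 44 to 51 days to spare.
- Slowest cohort 1 with fastest cohort 2: 139 − 135.4 = 3.6 days of delay at 4 per month; 139 − 150.6 = −11.6, no delay, at 24 in 9 months.

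**The case against.** The strongest reply is that the protocol already handles most of this. A reader of 16.1.1 alone might infer that cohort 3 can open without regard to cohort 1. Section 5.4 rules that out, because safety must be confirmed in both earlier cohorts. A reader might also infer that cohort 3 will open on immature data. The calendar says otherwise: the wait for the cohort 2 review normally outlasts the 44 days, so a wrong pass would require the reviewers to overlook data already on file. This stands and limits the weight of the point.

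The larger probabilities are also tempting. They require either leaving out an unresolved grade 3 event, or cutting each patient at her own end of chemoradiation with no later look. Section 16.1.1 states neither, and a per-patient cut fits poorly with a cohort-level count. They show why a data cut should be written down; they are not the expected effect.

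Even accrual is a further assumption. Cohort 1 needs four patients per radiation field, so actual spacing may differ, and slower accrual shrinks the problem.

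What survives is that the only cohort 1 analysis the plan defines is placed too early for its own criterion, and no text requires it to be updated.

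**Conclusion.** The concern holds in a limited form and should be fixed. The stated timing falls short of the persistence criterion in the same section and of the 30-day window in 16.1 and 16.2. The resulting error can only favour passing.

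On the ordinary reading it is modest: about 3 to 4 percentage points at an assumed 20% rate and about 5 to 7 at 30% or 40%. These figures depend on the assumed rates, the constant hazard, even accrual, and 28-day induction with 42-day chemoradiation. The follow-up counts depend only on accrual pattern and equal treatment lengths.

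Two conflicts bear on the same gate. Section 16.1.1 says that exceeding the cohort 1 limit keeps the following cohort closed, yet also frees cohort 2 from the cohort 1 review, so it is unclear which cohort the limit blocks. Sections 16.1 and 16.4 also give different acute windows, 30 days and six months.

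**What to change.** In 16.1.1:
- Keep the look at the end of chemoradiation.
- State that the cohort 1 determination used to open cohort 3 rests on cohort 1 data through 44 days after the last cohort 1 patient completes chemoradiation.
- State that any grade 3 or higher event still open at that point is followed to resolution or to day 14 before it is counted.
- Reconcile, within 16.1.1 and with 5.4, which cohort the cohort 1 limit blocks.
- Reconcile 16.1 with 16.4 on the acute window that applies to this gate.

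**Cost.** Normally there is no delay, because cohort 3 already waits for the cohort 2 review, with 28 to 51 days to spare at equal treatment lengths. The worst combination at 4 per month costs about 4 days. Using the ±3-day dosing window for the second induction dose, at opposite ends in the two cohorts, could add up to 6 more (3.6 + 6 = 9.6 days).

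This low cost holds for the 30-day window only. A six-month window would hold cohort 3 for 182 + 14 − (72.4 to 79.4) = 117 to 124 days longer at 4 per month, or 196 − (87.6 to 94.6) = 101 to 108 days at 24 in 9 months, at equal treatment lengths.

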11 STUDY CALENDAR

Baseline evaluations are to be conducted within 28 days prior to start of protocol therapy, unless otherwise specified. Scans and x-rays must be done ≤4 weeks (28 days) prior to the start of therapy.

Assessments must be performed within 3 days prior to each treatment dosing day. Study assessments (required to be completed and resulted prior to any drug administration) and agents should be administered within ± 3 days of the protocol-specified date, unless otherwise noted.

The day an assessment (PE, labs, scan etc) is completed is day 0 for counting for example labs drawn on Friday can be used for Monday dosing as this is within 3 days

Baseline evaluations are to be conducted within 28 days prior to start of protocol therapy, unless otherwise specified below. Scans must be done <28 days prior to the start of therapy. Baseline labs are required within 14 days of registration. HCG is 7 days.						
Parameter	Pre- Study to be sent to BrUOG with results prior to registration	Weekly ^a within 3 days prior to dosing day 1 each week.	Monthly ^b required within 3 days prior to day 1 of each cycle	Off study (post completion of whole cycle) ^j +1 week	30 days post last treatment (+1 week) ^j	Follow-up
Informed consent(within 30 days of day 1) *pts are to be re-consented if ICF will be outside 30 day window	X					
Diagnostic pathology	X- no time frame					
FNA	X- no time					

BrUOG 355: 7/8/17, 7/11/17, 7/20/17, 8/7/17, 8/8/17, 8/14/17, 8/16/17, 8/21/17, 8/22/17, 8/24/17, 8/28/17, 9/5/17, 9/6/17, 9/8/17, 9/11/17, 11/7/17, 11/8/17, 11/19/17 approved DD, 11/20/17, 12/12/17, 12/14/17, 1/29/18, 2/1/18, 2/6/18, 2/7/18, 2/8/18, 2/9/18, 2/12/18, 2/13/18, 3/8/18 all reviews, 3/9/18, 3/13/18, 3/14/18, 3/15/18, 4/19/18, 4/23/18, 5/29/18, 6/5/18, Amendment # 1 7/9/18, Amendment # 2 12/12/18, Amendment #3, 4/6/2020, Amendment #4 5/11/2020

	frame k					
History & Physical	X	X	X	X	X	
Concurrent meds	X	X	X	X		
Toxicity Assessment	XD	X	X	X	X	
Vitals M	X	X	X	X		
Performance status	X	X	X	X		
Imaging evaluation(CT C/A/P preferred)	Xf			Xf	Xf	Xf
Tumor measurement	X			X		X
CBC (Including differential)	Xd	Xe	X	X		
Chemistries (CMP, CA/Mg/PO ₄)	Xd	X	X	X		
Amylase and lipase	Xd	X	X	X		
Liver Function tests (AST, ALT, Alk Phos, LDH)	Xd	X	X	X		
EKG	X					
Pregnancy test	Xg	Xg	Xg			
Audiogram	Xh		Xh	Xh		
Thyroid Function Tests (TSH, Free T4, T3)	X		X	X		

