Viral studies (CD4 count – only required for patients who are HIV positive to certify eligibility, see exclusion 3.2.2 for timeframes and requirements.; HBsAg, , HCV Ab, if positive HCV Ab then order HCV RNA testing)	X					
Tumor Biopsy	X ^c					
Radiation			X ^N			
Cystoscopy, proctoscopy, barium enema	X- optional but if done must submit					

CMP=Glucose, Calcium, Albumin, Total Protein, Sodium, Potassium, CO₂, Chloride, BUN, Creatinine, ALP, ALT, AST, Bilirubin (total), amylase and lipase

- a. Obtain during cycles 1 and 2 Nivolumab (all cohorts) and chemoradiation therapy. Amylase and Lipase are required within 3 days of dosing with Nivolumab, with cycles 1 and 2 and q 2 weeks during chemoradiation therapy.
- b. Obtain for those patients receiving maintenance nivolumab treatment, prior to dosing each cycle

BrUOG 355: 7/8/17, 7/11/17, 7/20/17, 8/7/17, 8/8/17, 8/14/17, 8/16/17, 8/21/17, 8/22/17, 8/24/17, 8/28/17, 9/5/17, 9/6/17, 9/8/17, 9/11/17, 11/7/17, 11/8/17, 11/19/17 approved DD, 11/20/17, 12/12/17, 12/14/17, 1/29/18, 2/1/18, 2/6/18, 2/7/18, 2/8/18, 2/9/18, 2/12/18, 2/13/18, 3/8/18 all reviews, 3/9/18, 3/13/18, 3/14/18, 3/15/18, 4/19/18, 4/23/18, 5/29/18, 6/5/18, Amendment # 1 7/9/18, Amendment # 2 12/12/18, Amendment #3, 4/6/2020, Amendment #4 5/11/2020

- c. The first tumor biopsy may come from the diagnostic procedure where the diagnosis of cervical cancer was made. For patients who consent, a second biopsy should be attempted within 7 days after second dose of nivolumab in all patients, prior to chemoradiation.
- d. Must be obtained within 14 days prior to initiation of protocol treatment
- e. If grade 4 neutropenia is documented, monitor CBC twice weekly until resolved to \leq grade 3
- f. CT C/A/P is the preferred method of imaging. CT C/A/P must be obtained at the completion of chemoradiation (+ 14 days), 6 months later (+/- 14 days) and then q 6 months (+/- 14 days) for up to 3 years or until confirmation of PD. If an alternative imaging modality is used at baseline, the same imaging technique must be used throughout the study duration.

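### The week-4 cohort 2 review comes too early to apply the 14-day persistence criterion to toxicity that begins after the first maintenance dose

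*Combined protocol and SAP*

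**What the plan says.** Section 16.1.1 defines the safety event as "Grade 3 or higher adverse events that persists for 14 days or longer despite dose-holds and/or maximal medical support". It leaves out uncomplicated neutropenia and "any laboratory abnormalities deemed by the treating clinician as having no clinical significance", so laboratory toxicity judged clinically significant does count. If more than 25% of a cohort has such an event ("more than 2 patients in cohort 1 or more than 1 patient in cohort 2"), the treatment is called not feasible and the next cohort is not opened.

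For cohort 2, "evaluation for safety will occur 4 weeks following initiation of maintenance nivolumab", and "the safety review will be completed for cohort 2, before enrollment begins in cohort 3".

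Section 11 has two on-treatment schedules. The footnote to the weekly column reads "Obtain during cycles 1 and 2 Nivolumab (all cohorts) and chemoradiation therapy". The monthly column is "required within 3 days prior to day 1 of each cycle", and its footnote reads "Obtain for those patients receiving maintenance nivolumab treatment, prior to dosing each cycle". Section 5.4 sets the cohort 2 maintenance cycle at 4 weeks with a window of 3 days either way, starting 2 to 3 weeks after chemoradiation.

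For cohort 3, Section 16.1.1 places the maintenance safety analysis after maintenance has ended. Section 5.4 plans that maintenance for 2 years.

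**The concern.** A criterion that needs 14 days of observation is applied at a review only 4 weeks after the exposure it is meant to judge. In the second half of that window no new event can meet the criterion. In the whole window there is one scheduled laboratory draw, at or near its end. A clinically significant grade 3 or higher laboratory value first found at that draw is known to the reviewers but is not yet a qualifying event. Read literally, the rule lets cohort 3 open with that event uncounted.

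This matters because the cohort 2 review is the only specified check on maintenance nivolumab before cohort 3 starts concurrent plus maintenance treatment. Hepatic, renal and endocrine events, which often show first in laboratory tests, are among the select adverse events that the protocol itself lists in Section 8.1.

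**Working it through.** **The plan's own figures.** 25% of 8 is 2 and 25% of 4 is 1, so the stated counts agree with the stated percentage. The rule stops at 3 of 8 (37.5%) in cohort 1 and at 2 of 4 (50%) in cohort 2. The cohorts sum to 8 + 4 + 12 = 24. No error rate is stated for the rule.

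**Inputs.** Persistence of 14 days and review at 4 weeks (16.1.1); 28-day cycle, plus or minus 3 days (5.4); laboratory tests up to 3 days before each maintenance cycle (11). Day 1 is the first maintenance dose, so the review is on day 29.

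**Step 1: latest onset that can qualify.** 29 − 14 = 15. An event starting after day 15 cannot reach 14 days by the review, whether it is symptomatic or laboratory, and however closely the patient is watched.

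**Step 2: what the scheduled draw can document.** Days documented = 29 − day of the pre-cycle-2 draw.
- Nominal: draw on day 29, 0 days.
- Earliest: dose 3 days early and draw 3 days before it, 29 − 3 − 3 = day 23, so 6 days.
- Latest: dose and draw on day 32, after the review, so no post-dose scheduled value is available.

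None of these reaches 14.

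**Step 3: what can still count in cohort 2.**
- Onset in induction or chemoradiation: most laboratory tests are weekly, so 14 days can be documented before maintenance starts.
- Grade 3 or higher at the end of chemoradiation and still so at the pre-maintenance draw: with a 14- to 21-day gap and the 3-day laboratory window, the span is 14 − 3 = 11 to 21 days.
- Grade 3 or higher at the pre-maintenance draw (day −2 to 1), with the dose given, and still so at the pre-cycle-2 draw (day 23 to 29): 23 − 1 = 22 to 29 − (−2) = 31 days.
- An unscheduled test by day 15: 29 − 15 = 14 days, which just qualifies.

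**Step 4: possible effect on the decision.** Let p be the true proportion of patients with a qualifying event and f the share visible as qualifying at the review. The documents give neither, so both are assumed. With q = p × f, P(2 or more of 4) = 1 − (1 − q)^4 − 4q(1 − q)^3.

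| p | f = 1 | f = 0.75 | f = 0.5 |
|---|---|---|---|
| 0.2 | 0.181 | 0.110 | 0.052 |
| 0.3 | 0.348 | 0.220 | 0.110 |
| 0.4 | 0.525 | 0.348 | 0.181 |
| 0.5 | 0.688 | 0.481 | 0.262 |

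Example: p = 0.3 and f = 0.5 give q = 0.15 and 1 − 0.522 − 0.368 = 0.110.

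**Step 5: when a pending event would be settled.** An event first documented on day 29 reaches 14 days on day 43, two weeks after the nominal review. One first documented on day 23 reaches it on day 37.

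**The case against.** A reader might infer that no laboratory toxicity can ever meet the criterion in cohort 2, that the count is zero by construction, or that 2 of 4 is unreachable. The documents do not support that. The criterion is not limited to onset in maintenance, and step 3 shows four routes by which a laboratory event can count.

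Nor does every test become less frequent in maintenance. Amylase and lipase are tied to nivolumab dosing in induction and are every 2 weeks during chemoradiation. Thyroid tests have no weekly entry at all. The fall from weekly to 4-weekly applies to blood counts, chemistries and liver tests.

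A second objection is that a grade 3 value would be rechecked. Section 5.5.1 turns on whether hepatic events improve within 5 days and whether thrombocytopenia exceeds 7 days, which implies repeat testing. Section 7.1.3 asks for weekly creatinine clearance once treatment is held. The Appendix D flowcharts, not visible in the copy reviewed, may ask for more. This stands as a reason to expect good follow-up, but it starts only on detection. A value first seen between day 23 and day 29 still cannot have 14 documented days by day 29. Continuous reporting under Section 8.5 can date symptoms, but not a silent abnormality before anyone drew blood.

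Third, Section 16.1.1 does not say whether week 4 is a date for each patient or for the cohort. If the review waits for the fourth patient, those treated earlier may have further draws. That is fair, but the last patient always lacks them and the text does not require waiting.

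Finally, the reviewers and the DSMB (Section 15) see all adverse events and could act outside the rule. That limits the practical risk. It does not repair a written rule that leaves the event uncounted.

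**Conclusion.** The mismatch is real but confined to toxicity with onset after the first maintenance dose. In that window, onset after day 15 cannot qualify by day 29. The single scheduled draw documents 0 to 6 days against the 14 required, or comes after the review if the dose is late. New, silent laboratory toxicity therefore cannot count toward the cohort 2 limit from scheduled tests alone.

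The day counts rest on the protocol's own windows and on a review at day 29. How often the decision would change cannot be derived from the documents. If 30% to 50% of patients truly had a qualifying event and half were visible as such at the review (both assumed), the chance of reaching 2 of 4 would fall from 0.35–0.69 to 0.11–0.26. Those figures are an illustration, not an estimate.

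**What to change.** In Section 16.1.1, state that any non-excluded grade 3 or higher event that is ongoing, or was last recorded as grade 3 or higher, at a cohort 2 patient's week-4 evaluation is pending. The cohort 2 review is not closed, and cohort 3 is not opened, until the event has either fallen below grade 3 or reached 14 days and been counted.

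The sponsor should also reconcile the review time, the persistence criterion and the maintenance assessment schedule. That includes saying whether the evaluation is per patient or per cohort, and whether it waits for a pre-cycle-2 draw that falls after day 29. The status of a patient taken off treatment still has to be established; Section 7.3 keeps patients removed for toxicity in follow-up.

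The cost is wording, plus up to about two weeks' delay of the cohort 2 review, and only when a pending event exists. No new monitoring schedule and no treatment rule is proposed. A missing repeat test should not by itself be scored as persistence: with 4 patients, two missed repeats would be enough to stop the trial.

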Immune mediated: Adverse events (both serious and non-serious) associated with nivolumab may represent immunologic etiology. Nivolumab must be held for suspected immune-mediated toxicities or severe/life-threatening AEs of particular interest (in Section 7.0) and immune-related toxicities (in Appendix D). Please review both Sections (7 and Appendix D) prior to infusion of nivolumab in any patient in whom immune-mediated toxicity is suspected.

If the investigator is unsure if a particular toxicity at least possibly represents an immune mediated toxicity to nivolumab, the treating physician should follow section 7 and appendix D and treat as immune mediated, until it is confirmed as not being immune mediated. Consultation with BrUOG is suggested in such situations. BrUOG will share information about the situation with the BrUOG Reviewer and PI and provide the site guidance, as available.

Removal from study (all cohorts):

Patients must discontinue nivolumab permanently for the following:

- Any Grade 2 drug-related uveitis or eye pain or blurred vision that does not respond to topical therapy and does not improve to Grade 1 severity within the re-treatment period OR requires systemic treatment
- Grade 3 drug-related thrombocytopenia > 7 days or associated with bleeding
- Any treatment delay resulting in no nivolumab dosing for > 6 weeks.
- Patients who discontinue nivolumab during definitive chemoradiation (cohorts one and three)
- Grade 4 drug-related endocrinopathy adverse events such as adrenal insufficiency, ACTH deficiency, hyper- or hypothyroidism, or glucose intolerance, hypophysitis.
- \geq Grade 4 hepatic AEs
- \geq Grade 4 skin toxicity (per Appendix D can delay or discontinue for grade 3. Must come off, as per this bullet for grade 4 skin)
- ALL OTHER treatment related grade 3/4 treatment related events with the following exceptions:
 - Grade 4 neutropenia \leq 7 days;
 - Grade 4 lymphopenia or leukopenia;
 - isolated Grade 4 electrolyte imbalances/abnormalities that are not associated with clinical sequelae and are corrected with supplementation/appropriate management within 72 hours of their onset;
 - Grade 3 hepatic AEs that return to Grade 2 or less within 5 days Of note, this overrides Appendix D
 - Skin toxicity \leq grade 3 that improves with steroid therapy. NOTE: Any rash consistent with Stevens-Johnson Syndrome or Toxic Epidermal Necrolysis requires permanent discontinuation of nivolumab.
 - Grade 3 renal toxicity (as per Appendix D)

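### Section 16.1.1 counts a grade 3 or higher event only if it lasts 14 days and has no item for death, so a quickly fatal event after chemoradiation is not counted towards the 25% limit

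*Combined protocol and SAP*

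**What the plan says.** Section 16.1.1 (Safety review) lists two criteria. The first is "Grade 3 or higher adverse events that persists for 14 days or longer despite dose-holds and/or maximal medical support", followed by its exclusions: "This excludes uncomplicated neutropenia and any laboratory abnormalities deemed by the treating clinician as having no clinical significance". The second is "Inability to complete chemoradiation within 8 weeks".

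Each criterion has its own decision rule with the same limit, more than 25% of patients, spelled out as more than 2 in cohort 1 or more than 1 in cohort 2. The toxicity rule repeats the duration condition, counting patients who "experience a grade 3 or higher adverse event that persists for 14 days or longer, despite dose-holds and/or maximal support". If either limit is exceeded, "the treatment will be considered not feasible and the next cohort will not be opened".

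Cohort 1 is reviewed at the end of chemoradiation. For cohort 2, "evaluation for safety will occur 4 weeks following initiation of maintenance nivolumab". Enrollment to cohort 2 does not wait for the cohort 1 review, but the cohort 2 review must be complete before cohort 3 enrolls.

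Three other places bear on the same decision. Section 5.4 opens cohort 3 once safety is confirmed in cohorts 1 and 2, without defining confirmation. Section 16.4 says that acute toxicities determine feasibility within each cohort and gives no duration condition. Section 16.3 allows cohort 3 enrollment to be revised in light of cohort 1 outcomes.

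**The concern.** The duration test applies to every grade from 3 upward. It suits an event that a patient lives through. It does not suit a fatal one: a patient who dies within days of onset never reaches day 14, so on the literal text the most severe outcome is not counted, while a grade 3 event lasting 14 days is.

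Section 16.1 makes acute toxicity the primary endpoint, and these are the only numerical limits in the plan that bear on whether cohort 3 opens. Cohort 3 gives nivolumab both during and after chemoradiation, to up to 12 patients. A rule with this role should say how a death is counted and not leave it to inference.

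**Working it through.** **Plan's own figures.** 0.25 × 8 = 2 and 0.25 × 4 = 1. More than 25% therefore means at least 3 of 8 in cohort 1 and at least 2 of 4 in cohort 2, which agrees with the counts printed in 16.1.1.

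**Where neither criterion applies.** In cohort 2, maintenance starts 2–3 weeks after chemoradiation ends (Section 5.4), and the review comes 4 weeks after that. This is 2 + 4 = 6 to 3 + 4 = 7 weeks after chemoradiation. The completion criterion is settled before that period begins, so only the toxicity criterion remains. A fatal event lasting under 14 days scores 0 on both.

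During chemoradiation the gap is smaller, because a death before completion can be read as inability to complete. The two limits are applied separately, however, so such a death is not added to the toxicity count.

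**Effect of counting deaths on the toxicity rule.** Deaths are non-progression grade 5 events under 14 days. Persistent events are in other patients.

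| Cohort | Deaths | Persistent events | As written | Deaths counted | Result changes? |
|---|---|---|---|---|---|
| 2 (limit >1/4) | 1 | 0 | 0/4 | 1/4 = 25% | No |
| 2 | 1 | 1 | 1/4 = 25% | 2/4 = 50% | Yes |
| 2 | 2 | 0 | 0/4 | 2/4 = 50% | Yes |
| 1 (limit >2/8) | 2 | 0 | 0/8 | 2/8 = 25% | No |
| 1 | 1 | 2 | 2/8 = 25% | 3/8 = 37.5% | Yes |

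In the last row, if the death came before completion, the completion rule would stand at 1/8. As written, neither limit would be exceeded.

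**How often the limit would be reached (assumed rates).** The documents give no event rates. Let p be the share of patients with a countable persistent event and d the share with a quickly fatal event and no persistent one. In cohort 2, the probability of at least 2 of 4 at a counted rate r is 1 − (1 − r)^4 − 4r(1 − r)^3, with r = p as written and r = p + d if deaths count. With d = 5%:

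- p = 5%: 1.4% becomes 5.2%
- p = 10%: 5.2% becomes 11.0%
- p = 15%: 11.0% becomes 18.1%
- p = 20%: 18.1% becomes 26.2%
- p = 25%: 26.2% becomes 34.8%

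The rise is 3.8 to 8.6 percentage points over this range. With d = 0 there is no change.

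**Against Section 16.4.** That section summarizes acute toxicities by maximum grade and uses them to determine feasibility. A fatal event would be at the top of that summary and yet be absent from the 16.1.1 count.

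**The case against.** The strongest reply is that the two percentage rules are not the whole decision. They say when the next cohort must stay closed; they do not say that it must open otherwise. A reader might infer that a count of 0 opens cohort 3, or that 16.1.1 is the only gate. The documents do not support either. Section 5.4 requires safety to be confirmed, Section 16.4 has no duration condition, and the wording of 16.1.1 introducing the criteria is not exhaustive. The overall PI, the site PI and the medical director make the feasibility determination. The DSMB (Section 15) reviews all adverse events and can meet when needed, and Section 14.6 allows closure for unacceptable risk. All this stands, and it lowers the severity. It does not close the gap, because these routes are discretionary and none says how a death enters the count.

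One could also read a death as an event that persists. The text does not say so.

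A reader might go further and hold that every grade 4 event under 14 days must count too. The documents do not show the present choice to be an error. The criterion is aimed at toxicity that does not resolve under dose-holds and maximal support, an intelligible definition for a pilot study. Section 5.5.1 points both ways. It requires permanent discontinuation of nivolumab for events such as "Grade 4 drug-related endocrinopathy adverse events such as adrenal insufficiency", but it tolerates some brief grade 4 events (neutropenia of 7 days or less, and isolated electrolyte abnormalities corrected within 72 hours). Those rules act on the individual patient and not on cohort opening.

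Finally, an extreme such as 4 of 4 patients dying quickly and still scoring zero is a literal consequence of the text but not a realistic measure of the defect. Discretionary review would intervene long before that.

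**Conclusion.** The point holds for fatal events. On its literal wording, 16.1.1 does not count a non-progression death occurring less than 14 days after onset. In cohort 2 after chemoradiation, the second criterion cannot count it either. This also fails to match Section 16.4.

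The practical size is modest. The toxicity rule's outcome changes only where adding deaths brings the count to 2 of 4 or 3 of 8. Because cohort 2 opens whatever the cohort 1 review finds, a cohort 1 count can matter only for cohort 3. A single death would not trigger the rule even if counted, so nobody should read this point as saying that the rule would otherwise stop the trial after one death.

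The conclusion assumes the literal reading, in which death is not persistence. The scenario counts need no event rates; the probabilities rest on assumed ones. Severity: should be fixed, not must-fix.

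**What to change.** In 16.1.1, add to both the toxicity criterion and its decision rule that any grade 5 adverse event other than death from disease progression counts towards the 25% limit regardless of duration. The existing criterion has no attribution condition, so none needs to be added.

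Reconcile this with Sections 5.4 and 16.4: say whether confirmed safety in 5.4 means that the 16.1.1 limits were not exceeded in both cohorts, and whether the toxicities that determine feasibility in 16.4 are those counted in 16.1.1. The investigators should also state how grade 4 events shorter than 14 days are counted, whichever way they decide.

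The cost is a few sentences. No new data are needed: adverse events are graded under Section 8.2, and deaths on treatment or within 30 days are reportable under Section 8.7. The downside is that the not-feasible limit may be reached slightly more often, and only if such deaths occur.
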